4.2. Description of talimogene laherparepvec

The preparation and testing of the cell banks, viral seed stock, and talimogene laherparepvec clinical material were conducted in accordance with current Good Manufacturing Practices (cGMP), relevant the International Conference on Harmonisation of Technical Requirements for Registration of Pharmaceuticals for Human Use²¹ guidelines, European Directives, and the U.S. Pharmacopeia and Title 21 Code of U.S. federal regulations. In particular, the European Pharmacopoeia (Ph Eur) monograph on viral vaccine testing, ICH considerations on oncolytic viruses, and U.S. Food and Drug Administration (FDA) Points to Consider – Characterization of Cell Lines Used to Produce Biologicals (1993) have been followed for the safety testing of talimogene laherparepvec.

Talimogene laherparepvec has been extensively characterized using growth curves, buoyant density gradients, restriction mapping, size exclusion chromatography, epitope mapping, Western blotting, and electron microscopy. Additionally, the talimogene laherparepvec genome has been sequenced (Figure 3). Talimogene laherparepvec has been formulated in phosphate buffered saline (PBS) and a sugar stabilizer for direct intratumoral injection. The talimogene laherparepvec formulation is summarized in Table 1.

Figure 3: Schematic diagram of Talimogene laherparepvec

The sequenced result of talimogene laherparepvec

Table 1: Talimogene laherparepvec formulation

Talimogene laherparepvec is intended for direct injection into suitable non-neurological solid tumors. Dose schedules may vary for different tumors and indications. The initial dose should usually be lower than subsequent doses.

Name of ingredients	Quantity per mL	Function	Reference to standards
Active substance: talimogene laherparepvec	1×10^6 PFU or 1×10^8 PFU	Active	In-House Standard
Excipients: Phosphate buffered saline (PBS) pH 7.2	To 1.0 mL	Buffer	USP
sorbitol	20 mg	stabilizer	USP
myo-inositol	40 mg	stabilizer	USP

4.3. Drug supply and storage

Talimogene laherparepvec is provided as a sterile frozen liquid in a single-use 2.0 mL cyclic olefin polymer plastic resin vial. Each vial contains talimogene laherparepvec at a nominal concentration of 10^6 plaque forming unit (PFU)/mL or 10^8 PFU/mL in solution for intratumoral injection. Talimogene laherparepvec doses (1 mL extractable volume) will be applied. Vials will be sealed with elastomeric stoppers (with a fluoropolymer laminated plug and a crosslinked silicon top), and an aluminum seal with a flip-off dust cover. The vial caps are color coded to easily distinguish between the 10^6 PFU/mL (light green) and 10^8 PFU/mL (royal blue) vial concentrations.

Talimogene laherparepvec should be stored away from light and according to the storage and expiration information provided on the label that is affixed to the package containing the investigational product.

Talimogene laherparepvec should be thawed per the instructions provided in the Appendices section 15.7 and/or the package insert in Appendix P in PDOL. Vials should be checked for cracks or damage that may occur during the thawing process if not performed properly. Damaged

product should not be administered and after confirmation from Amgen, damaged vials should be destroyed on site.

4.4. Effects of talimogene laherparepvec in human

4.4.1. Talimogene laherparepvec clinical study

Fifteen clinical studies have been or are being conducted with at least 1 subject enrolled as of 30 June 2015. Seven studies are complete, 7 studies are ongoing, and 1 was terminated early.

Among the ongoing studies is the non-interventional registry study to investigate the long-term survival and safety of subjects previously treated with talimogene laherparepvec in any study. In addition to these 15 studies, two expanded access protocols, one each in the US and EU, are also ongoing.

Table 2: Summary of clinical studies

Study Number	Study Title	Study Status	Dose, Duration	Number of Subjects
Various Tumor Types				
001/01	First Administration to Man of an Oncolytic Herpesvirus-1 Vector Containing A Transgene For Granulocyte Macrophage Colony Stimulating Factor (OncoVEX ^{GM-CSF}): A Study of its Safety, Biodistribution and Biological Activity	Complete	Part 1: 10 ⁵ , 10 ⁷ , 10 ⁸ PFU/mL Single dose, dose-escalation study Part 2: A: 10 ⁶ , 10 ⁷ or 10 ⁸ , 10 ⁷ or 10 ⁸ PFU/mL (Seronegative subjects) B: 10 ⁶ , 10 ⁸ , 10 ⁸ PFU/mL or 10 ⁸ , 10 ⁹ , 10 ⁸ PFU/mL (Seropositive subjects)	Part 1: 13 Part 2: 17
			Up to 3 doses; For seronegative subjects, the 2nd and 3rd doses were administered only after HSV-1 seroconversion evidence	
Melanoma				
002/03	A Phase 2 Study of the Efficacy, Safety, and Immunogenicity of OncoVEX ^{GM-CSF} in Patients with Stage IIIc and Stage IV Malignant Melanoma	Complete	10 ⁶ , 10 ⁸ PFU/mL 8 doses over 15 weeks; if biological activity was observed, an additional 16 doses could have been administered	50
002/03-E	An Extension Protocol for the Extended Use of OncoVEX ^{GM-CSF} for Eligible Patients Participating in Study 002-03: A Phase 2 Study of the Efficacy, Safety and Immunogenicity of OncoVEX ^{GM-CSF} in Patients with Stage IIIc and Stage IV Malignant Melanoma	Complete	10 ⁸ PFU/mL Every 2 weeks until discontinuation criteria were met	3

Study Number	Study Title	Study Status	Dose, Duration	Number of Subjects
Melanoma				
005/05 ^a	A Randomized Phase 3 Clinical Trial to Evaluate the Efficacy and Safety of Treatment with OncoVEX ^{GM-CSF} Compared to Subcutaneously Administered GM-CSF in Melanoma Patients with Unresectable Stage IIIb, IIIc and IV Disease	Complete	10 ⁸ PFU/mL followed by 10 ⁸ PFU/mL Every 2 weeks until protocol-specified criteria were met	436 enrolled ^b : 295 talimogene laherparepvec 141 GM-CSF
005/05-E	An Extension Protocol to Evaluate the Efficacy and Safety of Extended Use Treatment with OncoVEX ^{GM-CSF} for Eligible Melanoma Patients Participating in Study 005/05	Complete	10 ⁸ PFU/mL followed by 10 ⁸ PFU/mL Every 2 weeks until protocol-specified criteria were met	31 enrolled: 28 talimogene laherparepvec 3 GM-CSF
20110264 ^c	A Phase 1b/2, Multicenter, Open-label Trial to Evaluate the Safety and Efficacy of Talimogene Laherparepvec and Ipilimumab Compared to Ipilimumab Alone in Subjects With Previously Untreated, Unresectable, Stage IIIb-IV Melanoma	Ongoing. Phase 1 fully enrolled, Phase 2 Open	10 ⁸ PFU/mL followed by 10 ⁸ PFU/mL every 2 weeks until protocol-specified criteria were met, with the addition of ipilimumab 3mg/kg every 3 weeks x 4 doses starting at week 6	Phase 1b: 19 enrolled. Phase 2: 200 (planned)
Study Number	Study Title	Study Status	Dose, Duration	Number of Subjects
Melanoma				
20110265	A Phase 1b/3, Multicenter, Open-label Trial of Talimogene Laherparepvec in Combination With Pembrolizumab (MK-3475) for Treatment of Unresected, Stage IIIB to IVM1c Melanoma (MASTERKEY-265)	Ongoing	Phase 1b: . 10 ⁸ PFU/mL followed by 10 ⁸ PFU/mL 21 days later. Subsequent doses of 10 ⁸ PFU/mL are administered every 2 weeks. Pembrolizumab: 200 mg -every 2 weeks.	Phase 1b: 21 enrolled Phase 3: 660 (planned)
			Phase 3: 10 ⁸ PFU/mL followed by 10 ⁸ PFU/mL 21 days later. Subsequent doses of 10 ⁸ PFU/mL are administered every 2 weeks until week 9 and every 3 weeks thereafter. Pembrolizumab: 200 mg every 3 weeks	

Study Number	Study Title	Study Status	Dose, Duration	Number of Subjects
Melanoma				
20110266	A Phase 2, Multicenter, Randomized, Open-label Trial Assessing the Efficacy and Safety of Talmogene Laherparepvec Neoadjuvant Treatment Plus Surgery Versus Surgery Alone for Resectable, Stage IIIB to IVM1a Melanoma	Ongoing	Arm 1: 10 ⁶ PFU/mL followed by 10 ⁸ PFU/mL 28 days later. Subsequent doses of 10 ⁸ PFU/mL are administered every 2 weeks until protocol-specified criteria are met. Surgery follows. Arm 2: Surgery alone.	75 per arm (planned)
20120139	A Registry Study to Evaluate the Survival and Long-Term Safety of Subjects with Melanoma Who Previously Received Talmogene Laherparepvec	Ongoing	Not Applicable	Not applicable
20120166	A Phase 3b, Multicenter, Open-label, Single-arm, Expanded Access Protocol of Talmogene Laherparepvec for the Treatment of Subjects With Unresected, Stage IIIB to IVM1c Melanoma	Ongoing	10 ⁶ PFU/mL followed by 10 ⁸ PFU/mL 21 days later Subsequent doses administered every 2 weeks until protocol-specified criteria were met	100 (planned)

Study Number	Study Title	Study Status	Dose, Duration	Number of Subjects
Melanoma				
20120324	A Phase 2, Multicenter, Single-arm Trial to Evaluate the Biodistribution and Shedding of Talmogene Laherparepvec in Subjects With Unresected, Stage IIIB to IVM1c Melanoma	Ongoing	10 ⁶ PFU/mL followed by 10 ⁸ PFU/mL Second dose administered 21 days after the initial dose, subsequent doses administered every 2 weeks until protocol-specified criteria were met	50 to 60 (planned)
20120325	A Phase 2, Multicenter, Open-label, Single-arm Trial to Evaluate the Correlation Between Objective Response Rate and Baseline Intratumoral CD8+ Cell Density in Subjects With Unresected Stage IIIB to IVM1c Melanoma Treated with Talmogene Laherparepvec	Ongoing	10 ⁶ PFU/mL followed by 10 ⁸ PFU/mL 21 days later. Subsequent doses administered every 2 weeks until protocol-specified criteria were met	110 (planned)

Study Number	Study Title	Study Status	Dose, Duration	Number of Subjects
Pancreatic Cancer				
005/04	Targeted Delivery of OncoVEX ^{GM-CSF} by Endoscopic Ultrasound (EUS)-Guided Fine Needle Injection (FNI) in Patients with Irresectable Pancreatic Cancer: A Pilot Multinational Experiment on Safety and Proof of Concept	Complete	4 cohorts each received 3 doses, each 3 weeks apart: 1) 10^4 , 10^5 , 10^6 PFU/mL 2) 10^5 , 10^6 , 10^7 PFU/mL 3) 10^6 , 10^7 , 10^8 PFU/mL 4) 10^6 , 10^8 , 10^8 PFU/mL	17
Head and Neck Cancer				
004/04	An Exploratory Study Of The Safety And Biological Activity Of OncoVEX ^{GM-CSF} In Combination With Radiotherapy And Cisplatin In The Treatment Of Locally Advanced Epithelial Cancer Of The Head And Neck	Complete	4 cohorts each received 4 injections once every 3 weeks: 1) 10^6 , 10^6 , 10^6 , 10^6 PFU/mL 2) 10^6 , 10^7 , 10^7 , 10^7 PFU/mL 3) 10^6 , 10^8 , 10^8 , 10^8 PFU/mL 4) 10^8 , 3 additional doses up to 10^8 PFU/mL	17
006/09	A Phase 3 Randomized Trial of Concurrent Cisplatin and Radiotherapy with or without OncoVEX ^{GM-CSF} in Previously Untreated Patients with Locally Advanced Squamous Cell Carcinoma of the Head and Neck	Study terminated	10^6 PFU/mL followed by 10^8 PFU/mL	528 (planned) 5 enrolled: 2 talimogene laherparepvec 3 standard of care

DRR = durable response rate, GM-CSF = granulocyte macrophage colony stimulating factor, HSV = herpes simplex virus, OS = overall survival, PFU = plaque-forming units.

^a Data cutoff for primary analysis for DRR is 21 December 2012; data cutoff for primary analysis for OS is 31 March 2014.

^b 439 randomizations occurred, but one subject was later determined to have been randomized 3 times (at 3 different sites) and was therefore excluded from the ITT set.

^c Data cutoff for 20110264 (Phase 1b portion) is 05 May 2014.

*NCT numbers: 005/04: NCT00402025; 005/05: NCT00769704; 006/09: NCT01161498

4.4.2. Pharmacodynamics and pharmacokinetics in humans

In previous clinical studies of talimogene laherparepvec, samples were taken at protocol-specified times before and after talimogene laherparepvec was administered to assess viral shedding, biodistribution, and the sero-status of patients with regard to HSV. Occasionally, investigational swabs and tissue samples (biopsies) were analyzed for the presence of talimogene laherparepvec at the request of the investigator.

4.4.3. Safety and efficacy of talimogene laherparepvec in phase 1 study of solid tumor

Study 001-01 was a phase 1, open-label study to evaluate the safety, biodistribution, and biological activity of 3 dose levels of talimogene laherparepvec in patients with advanced solid tumors with metastases in the skin or subcutaneous tissue. In part 1 of the study, a single dose of talimogene laherparepvec was administered to cohorts of 4 patients. The first dose group received talimogene laherparepvec at a dose of 10^6 PFU/mL, the second dose group received 10^7 PFU/mL, and the third dose group received 10^8 PFU/mL. In part 2 of the study, the patients received up to 3 doses administered every 14 days at the following 3 dose levels: group A received 10^6 , 10^7 , and 10^7 PFU/mL; group B received 10^8 , 10^8 , and 10^8 PFU/mL; and group C received 10^6 , 10^8 , and 10^8 PFU/mL. The investigational product was administered directly into a cutaneous or subcutaneous tumor.

Thirty patients participated in the study. Of those, 14 had adenocarcinoma of the breast, 9 had malignant melanoma, 4 had squamous cell carcinoma of the head and neck, and 3 had various other solid tumors. A total of 8 patients withdrew from the study prematurely: 3 (10%) withdrew

owing to progressive disease, 2 (6%) withdrew owing to serious adverse events, 1 (3%) withdrew consent, and 2 (6%) withdrew for other reasons.

Almost all the patients (29 of 30; 97%) experienced at least 1 adverse event during the study. Most of the adverse events reported were mild or moderate in severity. The most commonly reported adverse events across all treatment groups were pyrexia (19 patients; 63%), neoplasm progression (9 patients; 30%), rigors (8 patients; 27%), post-procedural complications (8 patients; 27%), nausea (7 patients; 23%), anorexia (7 patients; 23%), vomiting (6 patients; 20%), and injection site reaction (6 patients; 20%).

Of 30 patients, 16 (53%) had serious adverse events. The most frequently reported serious adverse events were neoplasm progression (13%), post-procedural complications (13%), pyrexia (13%), dyspnea (10%), and injection site reaction (7%). All other serious adverse events were reported in one patient each. Two patients withdrew from the study prematurely owing to serious adverse events, and 5 deaths were reported; of those deaths, 3 were attributed to disease progression, 1 to aspiration pneumonia, and 1 to an accidental overdose of analgesia.

There was no meaningful difference in the overall incidence of adverse events following the first and second injections, with 27 of 30 patients (90%) reporting adverse events after the first injection and 13 of 15 patients (87%) reporting adverse events after the second injection. There was, however, a reduction following the third injection, with 11 of 15 patients (73%) reporting adverse events.

In the first 2 single-dose groups (10^6 and 10^7 PFU/mL), the 4 patients (3 receiving 10^7 PFU/mL and 1 receiving 10^6 PFU/mL) who were seronegative to HSV-1 at study entry all developed flu-like symptoms such as fatigue, rigors, and pyrexia as well as erythema around the injected lesion. Two seronegative patients who received talimogene laherparepvec at 10^7 PFU/mL developed an erythematous rash with scattered vesicles in the skin. Shedding of the virus from some of the injected nodules also occurred; however, the virus was not detected on the outer dressing of the injection site. The events were transient and self-limiting, and no sequelae were noted. It was therefore concluded that seronegative patients should receive a lower initial dose (i.e., 10^6 PFU/mL) of talimogene laherparepvec.

In analyses to detect virus via specific quantitative PCR in blood, results were positive at one or more time points for 10 of 30 patients. Urine was positive for virus at one or more time points for 2 patients. Generally, in the repeated-dose part of the study, virus was noted only within 8 hours after the injection.

Four patients experienced shedding of live virus from the injection site, although in all cases, this was contained within the occlusive dressing, and no virus was detected on swabs of the outside of the dressing. Three of these patients were seronegative at baseline; 2 of the patients were given a first dose of talimogene laherparepvec at 10^7 PFU/mL, 1 received 10^8 PFU/mL, and 1 received 10^6 PFU/mL. Three patients had transient cutaneous vesicles or vesicle-like areas at various sites including the mouth, nose, forehead, cheek, right buttock, back, and sternum during weeks 2 and 3 of the study. Two of these patients were seronegative for HSV1 at enrollment and given a single dose of talimogene laherparepvec at 10^7 PFU/mL. The third patient who had vesicle-like areas was also seronegative at enrollment and was given 3 doses of talimogene

laherparepvec (10^6 PFU/mL, 10^7 PFU/mL, and 10^7 PFU/mL). Swabs were taken from these sites, but no virus was detected. In subsequent studies, a first dose of 10^6 PFU/mL has been administered, followed by higher doses of 10^8 PFU/mL, after this higher dose shedding is seen only rarely. Swabs were also taken from sites other than the injected nodule for 4 additional patients, and virus was not detected in any of these patients.

The secondary objective of the study was to identify signs of biological activity of the virus in the treated patients. Tumor response was assessed using Response Evaluation Criteria in Solid Tumors (RECIST; version 1.1).

Eight patients (27%) had stable disease, 19 patients (63%) had progressive disease, and 3 (10%) were not evaluable. In addition to tumor assessments, the study also defined a response if tumor necrosis was seen in a biopsy. Nineteen patients had biopsies containing tumor tissue. Of these, 13 biopsies (68%) showed evidence of partial or extensive tumor necrosis. One additional tumor-containing biopsy showed apoptosis. Thus, 14 of 19 patients (74%) with biopsies containing tumor tissue had necrosis or apoptosis.

HSV was detected by the use of a polyclonal antibody to stain biopsies taken from talimogene laherparepvec-injected tumors. Virus was shown to co-locate with areas of necrosis in the tumor; all biopsies with necrosis stained strongly for HSV. Non-necrotic and non-tumor tissues in the biopsies very rarely stained for HSV.

Tumor biopsies were stained for a variety of T cells (expressing CD3, CD4, CD8, CD30, and CD68 markers). All biopsies were positive for these cells. However, no obvious patterns emerged and, in the absence of baseline data, it is not possible to conclude that T cell levels were elevated as a result of treatment.

Quantitative PCR also was performed to evaluate the presence of hGM-CSF mRNA in order to measure talimogene laherparepvec –encoded GM-CSF versus endogenous GM-CSF. Of 13 biopsies with partial or extensive tumor necrosis, 11 (84.6%) showed measurable quantities of talimogene laherparepvec encoded GM-CSF mRNA, and the level of mRNA expressed was dose dependent (i.e., more GM-CSF mRNA was expressed after administration of higher doses of talimogene laherparepvec). Additionally, seronegative patients expressed more GM-CSF mRNA than did seropositive patients.

4.5. Registration and marketing experience

Talimogene laherparepvec has received regulatory approval for marketing in US and Europe.
US:

Talimogene laherparepvec is approved in melanoma. Intralesional injection of talimogene laherparepvec, also known as IMLYGIC®, has been approved by the United States Food and Drug Administration (FDA) for the local treatment of unresectable cutaneous, subcutaneous, and nodal lesions in adult patients with melanoma recurrent after initial surgery. However, it has not been shown to increase OS or have an effect on metastases to internal organs including the liver and lungs.

Europe:

IMLYGIC® is indicated for the treatment of adults with unresectable melanoma that is regionally or distantly metastatic (Stage IIIB, IIIC and IVM1a) with no bone, brain, lung or other visceral disease the first oncolytic viral therapy. It is proposed that IMLYGIC®, be initiated and supervised by a qualified physician experienced in the treatment of cancer.

4.6. Important Identified and Potential Risks, Adverse Drug Reaction (ADRs)

Consult the current Investigator's Brochure (IB) for the full information on Identified and Potential Risks of talimogene laherparepvec and Adverse Drug Reaction (ADRs).

5.0. Patient eligibility

Up to 36 patients will be enrolled in the study. Patients must to meet the following criteria to be eligible for the study.

5.1. Inclusion criteria

5.1.1. Histologic confirmation of breast carcinoma.

5.1.2. Histologic confirmation of recurrence of chest wall / cutaneous, subcutaneous or nodal tumors disease with or without distant metastasis.

5.1.3 Patients must have failed at least 1 systemic regimen or have clinical stable disease with capecitabine, hormonal therapy (with or without mTOR inhibitor or CDK4/6 inhibitor), or anti HER-2 therapy (trastuzumab, pertuzumab, ado-trastuzumab emtansine, lapatinib) for at least 2 months after their diagnosis of locoregional/metastatic disease.

5.1.4. Concurrent radiation therapy is permitted after the study treatment is initiated so long as the planned radiation field doesn't overlap with planned injection sites.

5.1.5. Age 18 years or older.

5.1.6. Eastern Cooperative Oncology Group performance status (ECOG PS) 0-1

5.1.7. Adequate hematologic function

- Absolute neutrophil count $\geq 1.0 \times 10^9/L$. If patient is taking CDK4/6 inhibitor or capecitabine, there is a need for maintaining ANC ≥ 1.0 consistently for at least 2 months without dose changes.
- Platelet count $\geq 75 \times 10^9/L$. If patient is taking CDK4/6 inhibitor, ado-trastuzumab emtansine or capecitabine, there is a need for maintaining platelet count $\geq 75 \times 10^9/L$ without dose changes.
- Hemoglobin $\geq 8.0 \text{ g/L}$
- International normalization ratio (INR) or prothrombin time (PT)/ partial thromboplastin time (PTT)/ activated PTT (aPTT) $\leq 1.5 \times \text{ULN}$, unless the subject is receiving anticoagulant therapy, in which case PT and PTT/aPTT must be within therapeutic range of intended use of anticoagulants

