5.2 Exclusion criteria

5.2.1. Patients who have operable disease with curable intent, and/or are candidates for radiation therapy for local control.

5.2.2. Patients receiving concurrent anti-cancer therapy (chemotherapy except Capecitabine or ado-trastuzumab emtansine , immunotherapy) while taking the study medication, or have previously received talimogene laherparepvec or any other oncolytic virus.

5.2.3. Patients with metastatic sites that necessitate chemotherapy (except Capecitabine or ado-trastuzumab emtansine) .

5.2.4. Known active central nervous metastases. Subjects with previously treated brain metastases may participate provided they are stable (without evidence of progression by imaging for at least four weeks prior to the first dose of trial treatment and any neurologic symptoms have returned to baseline), have no evidence of new or enlarging brain metastases, and are not using steroids $> 10 \text{ mg/day}$ of prednisone or equivalent. The exception does not include carcinomatous meningitis which is excluded regardless of clinical stability.

5.2.5. More than three lesions per organ for visceral metastases except for lung or lymph node.

5.2.6. History or evidence of active autoimmune disease that has required systemic treatment (i.e., use of corticosteroids, immunosuppressive drugs or disease modifying agents)

Replacement therapy (eg, thyroxine for hypothyroidism, insulin for diabetes or physiologic corticosteroid replacement therapy for adrenal or pituitary insufficiency) is not considered a form of systemic treatment for autoimmune disease.

5.2.7. A concurrent disease or condition that would render the patient inappropriate for study participation or any serious medical disorder that would interfere with the patient's safety.

5.2.8. History of other malignancy within the past 5 years with the following exceptions:

- Adequately treated non melanoma skin cancer without evidence of disease at the time of enrollment
- Adequately treated cervical carcinoma in situ without evidence of disease at the time of enrollment
- Adequately treated breast ductal carcinoma in situ without evidence of disease at the time of enrollment
- Prostatic intraepithelial neoplasia without evidence of prostate cancer at the time of enrollment.

5.2.9. Active infection that necessitates intravenous or oral antibiotics.

5.2.10. Evidence of immune suppression as following:

- Known human immunodeficiency virus (HIV) infection or AIDS

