6.3. Dose management

Subjects should be assessed clinically for adverse events/toxicity prior to each dose using the Common Terminology Criteria for Adverse Events (CTCAE) version 4.0. Complete blood count with differential and chemistry panels including liver function laboratory tests (ALT, AST, and total bilirubin) should be obtained according to the schedule of assessment in the protocol, and

the results should be checked before each scheduled dose of talimogene laherparepvec. Dosing will occur only if these test values are acceptable per the protocol.

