8.0. Evaluation during study

The window for all assessments and treatments should be completed within 5 days of the scheduled time.

Patients will be allowed to continue current hormonal therapy, selected chemotherapy, targeted agents and/or anti-HER-2 therapy, which will be administered as standard of care, (per physician discretion) while receiving study drug.

8.1. Evaluation during talimogene laherparepvec:

- 8.1.1. Patients will have a CBC, differential count and platelet count before each cycle.
- 8.1.2. Patients may repeat the CBC, differential count and platelet count until recovery of these measures before the next cycle (absolute neutrophil counts \geq 1,000 and platelets \geq 100,000 per mm³).
- 8.1.3. Medical history and physical examination with vital signs, weight, and PS before cycles 2 and 5 and every additional 2 cycles of treatments.
- 8.1.4. Digital photography of chest lesions before cycles 2, 5, and every additional 2 cycles of treatment.
- 8.1.5. Toxic effects will be assessed before each cycle.
- 8.1.6. SMA (Na, K, BUN, creatinine, Mg, calcium, AST, ALT, glucose, LDH, and total bilirubin) will be performed before each cycle.
- 8.1.7. Levels of tumor markers (e.g., cancer antigen CA 27.29) will be assessed before cycle 5 and every additional 4 cycles of treatment.
- 8.1.8. Systemic immunity in serum or plasma levels of GM-CSF, IL-2, IL-12, TNF-alpha (α), IFN- alpha (α); and phenotype for T-cell subsets (CD3, CD4, CD8, CD25), and NK-cell subsets (CD16, CD56) will be determined via multiparameter FACS analysis (percentage and absolute numbers) before cycle 5 and at the end of study in [name] laboratory at MD Anderson.
- 8.1.9. PET-CT or CT of bone/ abdomen/chest should be performed before cycle 5 and before every additional 4 cycles of treatment as clinically indicated.
- 8.1.10. Disease assessment will be done at the end of cycle 4, cycle 8 and cycle 10.

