8.3 Study Calendar

Evaluation and treatment	Screening	Cycle 1 Day 1	Cycle 2 (D22+/-5 days)	Cycle 5 (D64 +/- 5 days)	Cycle 7 and every 2 cycles	Follow up⁹
Time	Baseline (within 6 weeks)	Prior to talimogene laherparepvec injection				
Eligibility, screening, consent, and registration	X					Patients will be monitored for 1 year after removal from the study or until death, whichever occurs first.
Medical history	X					
Staging with tumor measurements	X					
Photography of chest wall	X ¹		X	X	X	
Biopsy of local recurrence [HE, IHC]	X ⁸			X ⁸		
Biopsy of easily accessible distant metastasis [HE, IHC]				X ⁸		
Correlative immune study	X			X ⁷		
Physical examinations, vital signs	X	X ²	X	X	X	
ECOG PS	X	X ²	X	X	X	
Hematology assessment and Biochemical profiles ^{3,5}	X	X ²	X	X	X	
Tumor markers (CA27.29) ¹¹ , IgG (baseline only)	X			X	X ¹¹	
Chest X-ray; Breast sonography ¹³	X					
Pregnancy test if applicable ¹⁰	X					
PET-CT or CT scan of bone/abdomen/chest as clinically indicated	X			X	X ⁴	
Disease assessment ¹²				X	X	

Adverse events ⁵	X	X	X	X	X	
Talimogene Laherparepvec injection ⁶		X	X	X	X	

1. Within 1 week prior to treatment
2. No need to repeat if within 7 days from baseline
3. Hematology include CBC, differential count and platelet count; and biochemical profiles SMA include Na, K, BUN, creatinine, Mg, calcium, AST, ALT, LDH, total bilirubin
4. Repeat every 4 cycles as clinical indicated
5. Before each cycle. Reporting exposure to talimogene laherparepvec and should be collected for the duration of the study and safety f/u
6. Starting cycle 2, Talimogene Laherparepvec injection will be given every 2 weeks until disease progression
7. Correlative immune study will be repeated before cycle 5 and at the end of study if available.
8. Core biopsy of local recurrence at baseline if samples (i.e., paraffin block or 5-10 unstained slides) from the local recurrence are not available. Core biopsy of either distant metastasis or local recurrent lesions before cycle 5 based on patient status.
9. a. Safety Follow-Up: should be conducted approximately 30 days after the last dose of trial treatment or before the initiation of a new anti-cancer treatment, whichever comes first. Safety Follow-Up Visit can be done in the clinic, or by phone if patient is not willing to come to the clinic for follow up.
- b. Unexpected AEs: Patients removed from study for unexpected adverse events will be monitored until AE is resolved or stabilized.

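### The hemoglobin entry limit in 5.1.7 is given in g/L, ten times too low to exclude anyone; very probably a slip for g/dL

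*Combined protocol and SAP*

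**What the plan says.** Section 5.0 makes the listed criteria mandatory: "Patients must to meet the following criteria to be eligible for the study". Under "5.1.7. Adequate hematologic function" the protocol gives a floor for neutrophils, "Absolute neutrophil count $\geq 1.0 \times 10^9/L", then one for platelets, also per liter, and then the hemoglobin line: "Hemoglobin $\geq 8.0 \text{ g/L".

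Hemoglobin is not given a value anywhere else. Section 6.3 makes each dose conditional on the blood results: "Dosing will occur only if these test values are acceptable per the protocol". Section 8.1.2 describes what happens when counts are low: "Patients may repeat the CBC, differential count and platelet count until recovery of these measures before the next cycle". The recovery values that follow are 1,000 for neutrophils and 100,000 per mm³ for platelets, with none for hemoglobin. In the study calendar (8.3), footnote 3 names the tests without limits: "Hematology include CBC, differential count and platelet count".

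**The concern.** A hemoglobin floor is there to keep out patients too anemic to be treated safely. A floor of 8.0 g/L cannot do that, because no candidate would fall below it.

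The population makes the floor relevant. Under 5.1.3, patients have failed at least one systemic regimen or are stable on capecitabine, hormonal therapy or anti-HER-2 therapy, and 6.3.3 lets them continue these during the study. Section 5.1.7 adds stability conditions on neutrophils and platelets for patients taking certain of these drugs, so its authors meant blood counts to be a real screen.

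There is also a smaller point about classification. Section 9.7.3 places patients who do not meet eligibility among those not evaluable for response, and the analysis plan in 13.1 estimates the response rate in evaluable patients. Whether a patient who entered with marked anemia counts as eligible depends on the unit.

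**Working it through.** The check is a unit conversion and a search for any provision that supplies a different limit. The protocol derives no other figure from this one, so there is no calculation of its own to reproduce.

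**Inputs**

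- Limit as written: 8.0 g/L (5.1.7).
- Maximum enrollment: 36 (5.0 and 13.1).
- Conversion: 1 L = 10 dL, so the value in g/dL is the value in g/L divided by 10.

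**Conversion**

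1. As written: 8.0 g/L ÷ 10 = 0.8 g/dL.
2. The same number read in g/dL: 8.0 g/dL × 10 = 80 g/L.
3. Ratio: 80 ÷ 8 = 10.

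As an illustration, a candidate at 7 g/dL has 7 × 10 = 70 g/L. That passes the written limit (70 ≥ 8) and fails the probable intended one (70 < 80).

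**Does another provision supply the limit?**

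| Section | What it covers | Hemoglobin value? |
|---|---|---|
| 5.2.7 | Serious medical disorder or unsuitable condition, by judgment | None |
| 5.2.21, 5.2.22 | Recovery to CTCAE grade 1 from adverse events of earlier cancer therapy | None |
| 6.3 | Dosing conditional on acceptable blood results | None |
| 6.3.3 | Dose delay for treatment-related grade 3 or greater hematologic toxicity | None; acts after entry, not at screening |
| 7.2.5 | Blood count before treatment | None; the test is required but no limit is set |
| 8.1.2 | Recovery of counts before the next cycle | None; neutrophils and platelets only |
| 8.3, footnote 3 | Definition of the hematology tests | None |

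No row replaces the figure in 5.1.7. Section 6.3 refers back to limits in the protocol, and for hemoglobin the only one is the 8.0 g/L in question.

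**Effect on the design**

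The limit does not enter the two-stage response design, its error rates or expected sample sizes, or the toxicity stopping boundaries in 13.1. None of these changes.

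**The case against.** The strongest objection is that the protocol may not contain the error at all. The point rests on one missing letter, and the text was extracted from a PDF. Other places suggest lost or altered characters. The drug name in the repeated header of the form in 15.2 appears both with and without one of its letters. Table 2 gives the lowest Part 1 dose of study 001/01 as 10⁵ PFU/mL where 4.4.3 gives 10⁶. Some of these may be typing errors in the source, but a dropped letter cannot be ruled out. Against this, the extraction kept a per-deciliter unit intact in 5.2.13, and the hemoglobin line follows two per-liter limits, which makes an authoring slip easy to understand. The text alone cannot settle it. This part of the objection stands, and it is why the first step is to look at the source.

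The second objection is that the slip corrects itself: anyone applying a criterion for adequate blood counts would read 8.0 as g/dL, and nothing suggests that a site applied 0.8 g/dL. That is probably true, and it limits the practical impact. It does not make the written criterion right, since a new coordinator or an auditor has only the written limit to work from.

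Third, the protocol is not without protection. A blood count is required at screening, and 5.2.7 excludes "any serious medical disorder that would interfere with the patient's safety". Sections 5.2.21 and 5.2.22 would catch unresolved anemia caused by earlier treatment. These provisions narrow the gap. They do not close it, because 5.2.7 depends on judgment and the other two cover only adverse events of earlier cancer therapy.

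Finally, giving no on-treatment recovery value for hemoglobin in 8.1.2 may be deliberate, and it is not treated here as an error. It matters only because it means that 8.1.2 cannot supply the missing limit.

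**Conclusion.** The point holds. As written, the hemoglobin criterion is set at 0.8 g/dL, one tenth of the probable intended 8.0 g/dL, and excludes nobody. It is the only hemoglobin limit in the protocol.

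Three assumptions carry this conclusion:

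- The source document reads as the extracted text does.
- No ECOG 0-1 patient could have a hemoglobin below 0.8 g/dL. This is clinical common sense, not something the protocol states.
- The intended unit was g/dL. This is inferred, but no other reading gives a floor of 8.0 any function.

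The consequence is confined to safety screening and to the eligibility status of any enrolled patient whose baseline lies between 8 and 80 g/L. It is likely small in practice and does not touch the design's statistical properties. Confidence is moderate, because the source has still to be checked. If the source reads g/L, the criterion should be corrected.

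**What to change.** 1. Confirm the unit in the source protocol. If it already reads g/dL, nothing further is needed.
2. If it reads g/L, amend the hemoglobin line in 5.1.7 to at least 8.0 g/dL (80 g/L), stating both units.
3. In that case, compare the baseline hemoglobin of patients already enrolled, from the screening blood count in 7.2.5, with 8.0 g/dL. If any patient is below it, record how that patient will be classified under 9.7.3 before response is analyzed.

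The cost is one unit in an amendment and a look at results already collected for at most 36 patients. No new visits, tests or statistical changes are needed.
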